1.2 Theoretical framework

They say 'Use it or lose it' when it comes to the health of the brain. This is demonstrated by the finding that limb disuse and immobilization cause cortical changes (38,39). This might be caused by diminished afferent input. Many studies have shown that the absence of afferent input, caused by injuries, diseases, or anesthesia, leads to cortical reorganizations (40-44). Areas in the sensory and motor cortex that do not receive input, will be taken over by adjacent areas (42,44,45). This process reflects the plasticity of the brain, changes in peripheral structures can cause large cortical reorganizations (46). It is therefore suggested that absence of efferent output causes such cortical reorganizations too.

The fact that conservative treatment of DRF involves a longer period of immobilization, suggests that the immobilization itself is partly responsible for complaints as clumsiness and functional restrictions following DRF (30-32), which would mean that immobilization causes undesirable effects. The immobilization itself cannot be avoided, but the corresponding neural changes might be, by using motor imagery. Motor imagery is the mental state in which an individual performs an activity mentally and explicitly feels himself performing it, without actually performing the activity physically (47). This mentally rehearsing of activities and movements is used as treatment method of many diseases of the central nervous system, like Parkinson's Disease (48) and stroke (49-53). Although motor imagery training is found to be effective in

enhancing complex motor skills (54-56), strength (55,57), and reaction time (55) in athletes, little research has been published to determine the effect of motor imagery on recovery after peripheral injuries, such as a hand injury. One study provides evidence that motor imagery is beneficial in rehabilitation following immobilization after hand injury (31).

1.3 Hypothesis

[figure not shown]
We hypothesize that motor imagery training during the immobilization period improves functional outcome, specified as an increase in function, dexterity, grip strength and range of motion, and a decrease in pain.

2. OBJECTIVE

The objective is to determine whether motor imagery training during the immobilization period in DRF patients, leads to an improved functional outcome, specified as increasing function, dexterity, grip strength, range of motion, and decreasing pain.

3. STUDY DESIGN

The above hypothesis can be tested by conducting a parallel-group randomized controlled trial. The duration of this study is 5 weeks, depending on the length of the immobilization period. The patients will be measured during their visits to the hospital. The first measurement is conducted directly after removal of the cast. The second measurement is two weeks later, when the patients visit the hospital for their check-up appointment. A schematic view of the study is given below:

4. STUDY POPULATION

4.1 Population

Participants are selected among distal radius fracture patients who are conservatively treated by plaster cast, or by closed reduction followed by plaster cast, from the University Medical Center Groningen. Female patients aged between 45-75 years will be included, because DRF is most common in women of 45-75 years of age (58). Patients are excluded when the internal (first perspective) VMIQ-score is higher than or equal to 72 points. This indicates that they are unable to perform motor imagery adequately.

4.2 Inclusion criteria

- Distal radius fracture patients diagnosed after radiological assessment
- Female patients
- Aged between 45-75 years
- Conservative treatment by plaster cast, or closed reduction followed by plaster cast
- Low energy trauma caused by fall

4.3 Exclusion criteria

- Internal Visual Motor Imagery Questionnaire-score ≥ 72
- Intra-articular, communitive fractures of the distal radius
- Complications likely resulting in worse functional outcome (e.g. dislocation)
- High energy trauma (such as car accidents or by falls from height)
- Pre-existent upper-extremity disorders
- No understanding of Dutch language

4.4 Sample size

This is the first study that investigates the functional outcome effect of motor imagery training during the immobilization period in DRF-patients. Therefore, the sample size calculation cannot be based on data of an imagery intervention during immobilization on function after a DRF. In this study, function is the primary outcome variable, and it is measured using the Patient Rated Wrist/Hand Evaluation (PRWHE). This instrument is derived from the Patient Rated Wrist Evaluation (PRWE). The only difference between the PRWE and PRWHE is that the PRWHE contains extra questions about aesthetics. It still contains the originally validated questions,

format and scoring system. The added questions about aesthetics are not part of the scoring. Therefore, it can be treated as the PRWE (59). The PRWE is proven to be the most responsive instrument to measure outcome in DRF-patients (60), as it measures disability during usual and specific activities and also documents pain. Subjects can score from 0 to 100 on the PRWHE; 0 indicates no problems at all and 100 indicates large functional difficulties and severe pain. The sample size calculation will be based on the expected outcomes of motor imagery training on the PRWHE.

Description of calculation process

A previous study has described the change of the PRWE-score over time as a result of the process of natural recovery after a DRF (61). Based on the results of this study, a mathematical model was created using Matlab R2010a that estimates the PRWHE-scores between data collection moments. This way, a model was build to estimate the natural recovery process with respect to the outcome of the PRWHE. Using this model, it could be determined what the decrease of the PRWHE-score is, two weeks after cast removal. The results of this model showed that a decrease of 10 points can be expected between the first (T1) and second measurements (T2). This decrease is due to natural recovery, and therefore, we expect it to be present in both groups.

Based on expert's knowledge, we find a 1 week lead in the functional recovery of the motor experimental group on the control group a clinically significant difference. With use of the mathematical model, the change in the PRWHE-score after 1 week after cast removal could be estimated. Next, the mean standard deviation of the PRWHE-scores over time was calculated. By dividing the change in the PRWHE-score by the mean standard deviation, the effect size was calculated. Now, the sample size could be calculated using the statistical power analysis software G*Power 3 (62).

Effect size calculation

The model describing the change in the PRWHE-score as result of natural recovery following a DRF, showed that 1 week after cast removal a decrease of 5.3 points on the PRWHE can be expected, which indicates improved function. This would mean that the experimental group would show an extra decrease of 5 points on the PRWHE, two weeks after cast removal.

The mean standard deviation was calculated using the following formula:

$$\sigma = \sqrt{\frac{n_x^2 s_x^2 + n_y^2 s_y^2 - n_y s_x^2 - n_x s_y^2 - n_x s_x^2 - n_x s_y^2 + n_y n_x s_x^2 + n_y n_x s_y^2 + n_x n_y (\bar{X} - \bar{Y})^2}{(n_x + n_y - 1)(n_x + n_y)}}$$

This provided a mean standard deviation of 26.13... points.

The effect size was calculated using the following formula:

$$ES = \frac{\mu_1 - \mu_2}{\sigma}$$

This provided an effect size of 0.20...

Settings for sample size calculation

Test Family: F-tests

Statistical test: Repeated Measures ANOVA, within-between interaction

Effect size: 0.20

Significance level $\alpha = 5\%$

Preferred power = 80%

Number of groups: 2

Number of measurements: 2

Other settings were kept as the default setting.

Sample size calculation

The effect size, preferred power, significance level and two-tailed testing were entered in

G*Power 3. Running the program resulted in a calculated sample size of 52 patients.

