10.4 Benefits and risks assessment, group relatedness

Benefits

DRF is a very common injury, especially in elderly women (1-5). In most conservatively treated cases, the patients are immobilized by a plaster cast for 4 to 6 weeks (7). Immobilization can lead to muscle atrophy (8-10) and contractures (11). Research has shown that immobilization or limb disuse can cause cerebral reorganization and decreased excitability of the motor cortex (27-29,38), and therefore, can lead to deteriorated motor performance (77). During motor imagery, partly the same cortical areas are activated as during execution of movement (34-37). So, motor imagery might prevent such neural changes as cerebral reorganization and decreased excitability (31). Many studies to determine the effectiveness of motor imagery training are conducted in stroke patients, and these studies show that motor imagery is effective in regaining arm function (49,50,53,78). By making the patients do motor imagery training during the immobilization period, it is expected that these patients have a better outcome when their cast is removed. Hereby, these patients might recover more quickly, and possibly reach a better final outcome.

Risks

The risk of participation in this study is negligible. Measuring function and pain with use of respectively the PRWHE and VAS which are questionnaires, is not harmful to the patient. The measurement of ROM and grip strength is already part of the regular treatment protocol of DRF. Therefore, the measurements conducted in this study to determine ROM and grip strength will not provide a higher risk than the regular treatment protocol. The SODA is a test concerning the performance during activities of daily living. It is performed after cast removal when the medical treatment is completed. From that moment, the patients are advised to use their injured hand again, so it is improbable that the SODA will lead to a higher risk than the regular procedure. There are no studies found that determined the risks of motor imagery training. However, because the motor imagery training does not contain motion, it is highly unlikely that the intervention will be harmful.

The patients are measured twice, directly after cast removal and 2 weeks after cast removal. The measurements will take place during their regular visits to the hospital for a medical check, so this study does not require extra hospital visits.

Group relatedness

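### The sized difference is the first week's recovery placed two weeks after cast removal, the sized contrast may miss a lead gained in the cast, and 52 patients do not give 80% power for the stated one-week lead

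*Combined protocol and SAP*

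**What the plan says.** All of the sizing is in section 4.4 of the combined protocol and SAP.

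- **Relevant difference:** "we find a 1 week lead in the functional recovery of the motor experimental group on the control group a clinically significant difference".
- **Recovery model:** "1 week after cast removal a decrease of 5.3 points on the PRWHE can be expected". Over the two weeks between measurements, "a decrease of 10 points can be expected between the first (T1) and second measurements (T2"), and this natural recovery is expected in both groups.
- **Target:** "the experimental group would show an extra decrease of 5 points on the PRWHE, two weeks after cast removal".
- **Effect size:** "By dividing the change in the PRWHE-score by the mean standard deviation, the effect size was calculated". "This provided a mean standard deviation of 26.13... points", and the ratio is reported as 0.20 with further digits cut off.
- **Calculation:** G*Power, repeated-measures ANOVA, within-between interaction, effect size 0.20, alpha 5%, power 80%, two groups, two measurements, other settings at default. The result is 52 patients.

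Other sections bear on when the effect should appear. The Summary calls the design post-test only and places training in the immobilization period. Section 10.4 says of the trained patients that "it is expected that these patients have a better outcome when their cast is removed".

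**The concern.** There are three links between the stated clinical difference and the number 52, and each is weak.

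1. **Which week.** A group that is one week ahead at week 2 stands where the others will stand at week 3. Its lead is the week 2-3 fall. The week 0-1 fall equals it only if recovery is linear, and the plan's own figures point to slowing.
2. **Which contrast.** The interaction tests whether the groups change differently from T1 to T2. T1 is measured after training has ended. A benefit already present at T1 is a difference in level and need not show up as a difference in change.
3. **Which scale.** A difference divided by an SD is a Cohen's d. The F-test procedure takes Cohen's f.

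The stated 80% power is what justifies 52 patients. If it does not apply to the stated difference, a null result would say little about whether training gives a one-week lead.

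**Working it through.** **Reproducing the plan.** The default correlation is not stated. I assume 0.5 with sphericity, because this returns the plan's figure.

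- Effect size: 5.3 / 26.13 = 0.203. The 5 points given in the text yield 5 / 26.13 = 0.191, so 0.20 was formed from 5.3.
- Noncentrality: λ = f² × N × m / (1 − ρ) = 0.20² × 52 × 2 / 0.5 = 8.32, with 1 and 50 degrees of freedom. Power is 0.807, and 52 is the smallest even N that reaches 80%. The plan's figure reproduces.
- With 0.191 in place of 0.20 the same procedure needs N = 56.

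**Step 1: the week shift, within the plan's own convention** (difference/SD entered as f, ρ = 0.5).

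Week 1-2 fall: 10 − 5.3 = 4.7. The week 2-3 fall is not in the documents, so I extrapolate it as an assumption:

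- constant ratio: 4.7² / 5.3 = 4.17
- constant decrement: 4.7 − (5.3 − 4.7) = 4.1

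If the 10 is rounded from 9.5 to 10.5, week 1-2 is 4.2 to 5.2. The constant-decrement values are then 4.2 − 1.1 = 3.1 and 5.2 − 0.1 = 5.1.

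| Difference at T2 | Effect size | N for 80% | Power at 52 |
|---|---|---|---|
| 5.3, entered as 0.20 (plan) | 0.20 | 52 | 0.81 |
| 4.7 (week 1-2) | 0.18 | 64 | 0.72 |
| 4.17 | 0.160 | 80 | 0.62 |
| 4.1 | 0.157 | 82 | 0.60 |
| 5.1 (favourable end) | 0.195 | 54 | 0.79 |
| 3.1 (unfavourable end) | 0.119 | 142 | 0.39 |

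**Step 2: the contrast.** Suppose the whole one-week lead exists at T1 and both groups then follow the same curve. The gap is 5.3 at T1 and about 4.17 at T2. The control group falls 10 points from T1 to T2, and the experimental group falls 4.7 + 4.17 = 8.87. The interaction is 8.87 − 10 = −1.13, which is about 1.1 points in the unfavourable direction. With 26 per group and ρ = 0.5, power to detect it is about 5%, no more than alpha.

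If instead the groups are equal at T1 and the lead builds up afterwards, the interaction is the full extra decrease that section 4.4 describes.

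**Step 3: the scale.** Take that favourable scenario, an extra T1-T2 decrease of 5.3.

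- In a two-by-two layout an interaction of size δ moves each cell mean by δ/4, so f = δ / (4σ) = 5.3 / (4 × 26.13) = 0.051, not 0.20.
- λ = 0.0507² × 52 × 2 / 0.5 = 0.53, giving power of about 11%.
- Cross-check: at ρ = 0.5 the SD of change is 26.13 × √(2 × 0.5) = 26.13. A two-sample t-test on change with 26 per group has the same noncentrality, 0.203² × 26 / 2 = 0.53, and the same power.
- In reverse, f = 0.20 corresponds to an extra decrease of 0.20 × 4 × 26.13 = 20.9 points.
- The correlation matters but does not rescue the figure. Power for an extra 5.3 points is about 8% at ρ = 0, 15% at 0.7 and 21% at 0.8.

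**Direct comparison at T2** (two-sample t-test, two-sided 5%, SD 26.13, 26 per group): power is 11% for 5.3 points, 10% for 5.0, 10% for 4.7 and 9% for 4.17.

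**The case against.** The strongest defence is that the printed arithmetic is sound: 5.3 / 26.13 gives 0.20, and 0.20 gives 52. Which week should represent an expert-chosen lead is a modelling choice, and the 5 can be read as 5.3 rounded. That is fair, and the 5 against 5.3 is a minor inconsistency.

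Three stronger readings are tempting, and the documents do not support them.

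- **That 0.20 is overstated by a known amount.** The week 2-3 fall is not reported. At 5.1 points the effect size is 0.195 and N is 54, which is hardly a change. If the 10 were cut down from about 10.6, week 2 would equal week 1 (10.6 − 5.3 = 5.3) and there would be no slowing.
- **That the sized interaction has the wrong sign.** This holds only if the whole lead exists at T1. Section 4.4 describes an extra decrease after T1, which fits the chosen test, and section 10.4 goes on to say that patients might recover faster. The protocol does not say when the lead arises.
- **That the week shift explains the low power.** It does not. On a direct T2 comparison the shift moves power only from 11% to 9%. Most of the loss comes from entering a standardised mean difference as f.

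What the defence cannot answer is step 3. Even on the plan's own scenario, with its own 5.3 points and the default correlation, power is about 11%.

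**Conclusion.** The point stands in this form. Section 4.4 places the week 0-1 fall at week 2 without justification. Read literally, the one-week lead at T2 is probably smaller, with an effect size of about 0.16 (0.12 to 0.195), and within the plan's own convention power at 52 is about 0.60 to 0.62. That part rests on extrapolation and is small at the favourable end. Whether the interaction can show the benefit depends on when the lead arises, which is left open: the possibilities run from the full extra decrease to about −1.1 points.

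The firmest conclusion is about the stated power. For a T2 difference of 4.2 to 5.3 points, 52 patients give about 9 to 11%. For an extra T1-T2 decrease of 5.3 they give about 11% at correlation 0.5. Neither is 80%. These figures take the plan's SD of 26.13 as correct and assume 26 patients per group.

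**What to change.** In section 4.4:

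1. Read the week 2-3 fall from the existing recovery model and use it as the T2 target. Give the two-week fall to one decimal, and make the 5 and the 5.3 agree.
2. State whether the lead is expected at T1, at T2 or at both.
3. Name the between-group difference at T2 as the contrast that is sized, in place of the T1-T2 interaction.
4. Restate the effect size, labelled as d or f and converted correctly for that contrast, together with any correlation assumed.
5. Restate the power of 52 patients for that contrast.

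The cost is one read-out from a model the investigators already have, and some rewritten figures. The downside is that the stated power becomes much less favourable. No extra patients, visits or measurements are requested.

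### The SD of 26.13 behind the effect size is the total SD of two merged samples, not a mean SD; the error is probably small and conservative, and should be corrected only together with the conversion to Cohen's f

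*Combined protocol and SAP*

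**What the plan says.** Section 4.4 (Sample size) builds the effect size in three steps.

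- Numerator: a recovery model fitted to a published cohort predicts that "1 week after cast removal a decrease of 5.3 points on the PRWHE can be expected". The plan takes a one-week lead as the target and restates it as 5 points: "the experimental group would show an extra decrease of 5 points on the PRWHE, two weeks after cast removal".
- Denominator: "Next, the mean standard deviation of the PRWHE-scores over time was calculated". A formula is printed, followed by "This provided a mean standard deviation of 26.13... points". The numerator of that formula ends with the term n_x n_y (X̄ − Ȳ)². The section does not define X, Y, s or n, and does not say which visits they come from.
- Ratio: "This provided an effect size of 0.20". The G*Power settings then list "Effect size: 0.20" for a repeated-measures ANOVA, within-between interaction, with 2 groups, 2 measurements, alpha 5%, power 80% and other settings at default. The result is 52 patients.

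The same section expects a 10-point fall from the first to the second measurement through natural recovery, in both groups.

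**The concern.** A mean or pooled SD contains only the within-sample SDs. A formula that adds the squared difference in means measures the spread of everyone put together, including the gap between the samples. If X and Y are two time points, that gap is average recovery. The plan expects recovery in both groups, so it is not error in a comparison of groups. A comparison at one time needs the SD between patients at that time, and the interaction entered in G*Power rests on the SD of change. Neither contains the gap.

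Sigma is one of two inputs to the ratio, and any restated sample size will use it again. A wrong sigma would carry over into the repair of the rest of the calculation.

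**Working it through.** **Inputs.** From section 4.4: sigma 26.13, difference 5.3 (restated as 5), fall between measurements 10, effect size 0.20, alpha 5%, power 80%, 2 groups, 2 measurements. Assumed: the G*Power defaults are correlation rho = 0.5 and sphericity epsilon = 1.

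**1. Reproduce the plan.** 5.3 / 26.13 = 0.203. For the within-between interaction I used a noncentral F with df 1 and N − 2 and noncentrality λ = f² · N · 2 / (1 − rho).

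- f = 0.20, N = 52: λ = 0.04 × 52 × 4 = 8.32, power 0.807.
- f = 0.20, N = 50: power 0.791.

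So N = 52 reproduces. The unrounded 0.2028 gives 50, and 5 / 26.13 = 0.191 gives 56.

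**2. What the formula returns.** The variance of two merged samples is

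`[(n_x + n_y)((n_x−1)s_x² + (n_y−1)s_y²) + n_x n_y (X̄−Ȳ)²] / [(n_x+n_y−1)(n_x+n_y)]`

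Multiplied out, this is the printed expression, except that the available text shows − n_x s_y² twice where one should be − n_y s_y². That may be a text-extraction fault and has no effect when n_x = n_y. Two checks with n = 100 each:

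- SDs 25 and 22, means 10 apart: the printed formula and the merged-sample SD both give 24.017.
- SDs 20 and 20, means 30 apart: variance = (2 × 99 × 400 + 100 × 100 × 900 / 200) / 199 = 124,200 / 199 = 624.1, so the SD is 24.98, although both within-sample SDs are 20.

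**3. Remove the between-means term.** With equal and large n and equal SDs, s² = 26.13² − D²/4 = 682.78 − D²/4, where D is the difference between the source means. D = 10 is the plan's own fall between measurements; D = 20, 30 and 40 are assumptions. N is by the plan's method, from the unrounded ratio.

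| D | s | 5.3 / s | N |
|---|---|---|---|
| 0 (as stated) | 26.13 | 0.203 | 50 (52 at 0.20) |
| 10 | 25.65 | 0.207 | 48 |
| 20 | 24.14 | 0.220 | 44 |
| 30 | 21.40 | 0.248 | 36 |
| 40 | 16.82 | 0.315 | 22 |

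With 20 or 100 patients per source time point, D = 10 gives s = 25.97 or 25.71 and N = 50. With 20 per time point and the ratio rounded to 0.20, N stays at 52.

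**4. Direction.** The merged variance exceeds the within variance when D² > 2s²/n. At D = 10 this needs n > 2 × 682.78 / 100 = 13.7, so about 14 or more per source time point. Sigma is then too large, the ratio too small and N too large.

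**5. The next step in the same chain.** The F-test setting reads its input as Cohen's f, but 0.203 is a difference divided by an SD (d).

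- The usual two-group conversion is f = d/2 = 0.101.
- If the 5.3 points are a difference in change, the four interaction effects are ±5.3/4, so f = d/4 = 0.051.

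At N = 52 and rho = 0.5:

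| Sigma | f = d/2: power (N for 80%) | f = d/4: power (N for 80%) |
|---|---|---|
| 26.13 | 0.30 (194) | 0.11 (766) |
| 25.65 (D = 10) | 0.31 (186) | 0.11 (738) |
| 16.82 (D = 40) | 0.61 (82) | 0.20 (318) |

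No sigma in the range examined brings 52 patients to 80% once d is converted.

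**The case against.** The best defence has three parts.

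- **The mechanism is inferred.** The protocol never says that X and Y are time points. This stands. The phrase "the mean standard deviation of the PRWHE-scores over time was calculated" makes it the likely reading, but it is not stated. What does not depend on it is that the formula gives a merged-sample SD, whatever the samples are.
- **The documented effect is trivial and on the safe side.** This also stands. The only fall between two measurements that the plan gives is 10 points, which moves the ratio by 0.004. Part of the step from 52 to 48–50 is rounding, since the unrounded ratio already gives 50 with sigma as stated.
- **No arithmetic slip is shown.** True: 0.203 and 52 both reproduce. The fault is that the SD is not the quantity named, and not the one a group comparison needs.

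A reader might infer from the D = 20 to 40 rows that the trial needs far fewer than 52 patients. The documents do not support this. The model interpolates between the cohort's visits, so the source means may lie further apart than 10 points, but no value is given. A reader might also infer that the wrong SD leaves the trial underpowered. It does not: taken alone, it raises N.

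**Conclusion.** The point holds, with limited size. The 26.13 is not the mean SD it is called, because the printed formula adds the squared difference between two means. That recovery is the component added rests on reading X and Y as time points. With the plan's 10-point fall, equal n and equal SDs, sigma is about 25.65, the ratio is 0.207 instead of 0.203, and N is 48 to 50 instead of 52. Anything larger rests on an assumed gap between the source means.

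The error is conservative, so it gives no ground for saying that 52 is too few. Nor does correcting it give ground for saying that 52 is enough. The entry of d as f in the same calculation works in the opposite direction and is far larger: with 5.3/26.13, power at 52 is about 0.30 or 0.11 at an assumed correlation of 0.5, depending on the conversion.

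**What to change.** In section 4.4:

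1. State the source time points with their means, SDs and sample sizes.
2. Replace sigma with the pooled within-time SD, `sqrt([(n_x−1)s_x² + (n_y−1)s_y²] / (n_x+n_y−2))`, or with the SD at the source visit nearest the second measurement.
3. State the correlation between the two measurements, or the SD of change, because the interaction test needs it; do not leave it at a software default.
4. Use one numerator throughout, 5.3 or 5 points.
5. In the same revision, convert the ratio to Cohen's f for the effect being tested, and restate the effect size and the power at N = 52.

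Items 2 and 5 must go together, so that a lower SD is not used alone to support 52 or fewer patients. Replacing sigma is arithmetic on data the sponsor has already used. The correlation or SD of change may have to be an assumption with a range if the source does not report it. None of these steps changes trial conduct or data collection, but the restated power may raise the separate question of whether 52 is adequate.

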When this happens during immobilization after DRF, it will partly be responsible for complaints as clumsiness and functional restrictions that DRF-patients report (30-33). Motor imagery during the immobilization period might prevent (part of) these neural changes. Motor imagery is the mental process by which a subject performs an action mentally, and it has been found that during motor imagery, overlapping cortical areas are activated as during real execution of the same movement (34-37). So, motor imagery training of wrist movements during the

immobilization period following a DRF might prevent neural changes caused by limb disuse, which might underlie part of the remaining problems of these patients. Therefore, the aim of this study is to determine whether motor imagery training during the immobilization period following a DRF might prevent functional decay as result of limb disuse on short term. This might lead faster to a better functional outcome.

This study contributes to the existing knowledge of the effectiveness of motor imagery training, and it provides new knowledge about the effect of motor imagery during immobilization after peripheral injury. Furthermore, when it is found that motor imagery during immobilization following a DRF is beneficial, a simple and cheap rehabilitation method is found that can be used in addition to existing rehabilitation methods in treating DRF. When DRF-patients recover more quickly, health costs will decrease, and patients will be able to return to work and to normal daily activities earlier. This is an important aspect, because it is found that work related activities and recreational activities are affected most and the most prolonged (15,16).

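### Section 4.4 sizes the trial on a T1-to-T2 interaction from which a lasting benefit at cast removal cancels, 9.3 names no primary PRWHE contrast, and the 80% power rests mainly on a standardized difference entered as Cohen's f

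*Combined protocol and SAP*

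**What the plan says.** **Sizing (4.4).** The outcome is the PRWHE (0 best, 100 worst) and the clinically relevant effect is a one-week lead in recovery. The recovery model gives a natural fall of 10 points from T1 to T2, and states that "1 week after cast removal a decrease of 5.3 points on the PRWHE can be expected". From this the plan concludes that "the experimental group would show an extra decrease of 5 points on the PRWHE, two weeks after cast removal". On the effect size it says: "By dividing the change in the PRWHE-score by the mean standard deviation, the effect size was calculated". The SD is 26.13, the effect size 0.20, and the G*Power entry is "Statistical test: Repeated Measures ANOVA, within-between interaction" with two groups, two measurements, 5% significance, 80% power and all other settings at default. The result is 52 patients.

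**Timing.** Training takes place during immobilization. The Summary labels the design as post-test only. T1 is at cast removal (section 3), with the PRWHE taken by phone a day later (7.3). T2 is two weeks after cast removal.

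**Expected benefit.** The aim in 1.1 is that training "might prevent functional decay as result of limb disuse on short term". Section 10.4 says that "it is expected that these patients have a better outcome when their cast is removed", and also that "these patients might recover more quickly, and possibly reach a better final outcome".

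**Analysis.** Section 9.3 plans a MANOVA with factors group and time, reporting group differences at each visit for each variable, two-sided at 5%. It names no primary visit or effect. Section 7.1.1 makes the PRWHE the main parameter but gives no time point. Section 9.2 switches to Mann-Whitney when data are not normal. Section 7.1.3 lists six covariates.

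**The concern.** With two visits, the group-by-time interaction is the T2 group difference minus the T1 group difference. That contrast suits a trial whose first measurement is a baseline. Here T1 comes after the whole intervention, so it is already an outcome, and subtracting it removes whatever the training had achieved by then. The target in 4.4, an extra decrease by T2, implicitly takes the groups as equal at T1. Section 10.4 expects them to differ at T1.

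The only test with a stated power is therefore blind to one of the benefit patterns that the protocol anticipates. The comparisons that can see that pattern have no stated power and no order of priority. The T1 difference, the T2 difference, the overall group effect and the interaction could each be quoted as the PRWHE result, in a trial where neither patients nor researcher are blinded (7.2). Separately, readers will take the 80% at face value, and it does not apply to the 5-point target.

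**Working it through.** **Inputs.** From 4.4: SD 26.13, effect size 0.20, 5.3 points in the first week, 10 points over two weeks, 5-point target, N = 52. From 7.2: equal groups, hence 26 per group. The T1-T2 correlation r is not given. The G*Power default of 0.5 is assumed first, then 0.8 and 0.9. All powers are two-sided 5%, from the noncentral F.

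**1. Reproducing N = 52.** For the within-between interaction, λ = f²·N·m/(1 − r) = 0.20² × 52 × 2/0.5 = 8.32, with 1 and 50 df. Power is 0.807 (N = 50 gives 0.791), so the stated figure reproduces.

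**2. What f = 0.20 means.** A difference in change of d points enters the four cells as ±d/4, so f = d/(4·SD). Then f = 0.20 corresponds to d = 0.20 × 4 × 26.13 = 20.9 points. The plan's 0.20 is instead 5.3/26.13, a standardized mean difference. For 5 points the correct entry is f = 5/(4 × 26.13) = 0.048.

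**3. Cancellation.** With benefit a at T1 and b at T2, the interaction is b − a.
- If a = b, it is zero, and the rejection rate is 5% at any N and any r.
- If half of a 5-point benefit is already present at T1, b − a = 2.5. Power is 0.063 (r = 0.5) or 0.083 (r = 0.8).
- If a one-week lead is already held at T1, the T1 gap is the first week's natural fall, 5.3 points. One week later the gap is the second week's fall, 10 − 5.3 = 4.7. At T2 it is the third week's fall, which is not given. Assuming 4.0 to 4.7, the interaction is −1.3 to −0.6 points, with 5-6% power at r = 0.5 or 0.8.

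**4. Power for 5 points, benefit arising only after T1.** The SD of change is SD·√(2(1 − r)).

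| Contrast, SD 26.13 | Power at 26 per group | Per group for 80% |
|---|---|---|
| T2 difference | 0.104 | 430 |
| Interaction, r = 0.5 | 0.104 | 430 |
| Interaction, r = 0.8 | 0.188 | 173 |
| Interaction, r = 0.9 | 0.328 | 87 |

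The interaction reaches 80% at N = 52 only when r is 0.971. For 5.3 points the T2 difference has 0.111.

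**5. Range for the T2 SD.** The 26.13 is a mean over time, and its formula contains a squared difference between two means, so it may overstate the SD at one visit. For 5 points at T2, an assumed SD of 20 gives 0.143 and an SD of 15 gives 0.218. The difference detectable with 80% power is 20.70, 15.85 and 11.89 points at SD 26.13, 20 and 15.

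**6. Unranked PRWHE tests.** Simulation under no effect, 200,000 trials, each test at 5% with no gate:

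| r | T1 or T2 | T1, T2 or interaction |
|---|---|---|
| 0.5 | 0.090 | 0.123 |
| 0.8 | 0.078 | 0.119 |
| 0.9 | 0.071 | 0.113 |

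**The case against.** **A lasting benefit is not lost from the analysis.** A reader might infer that the trial cannot detect one. The documents do not support that: the per-visit comparisons in 9.3, and its group factor, keep it. It is lost only from the test that justifies N. This limits the point to a mismatch between the sized and the planned tests, but does not remove it.

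**The interaction is not an unreasonable choice.** It fits the extra decrease in 4.4 and the faster recovery that 10.4 also mentions. If the benefit arises only after T1 and r exceeds 0.5, it is the more powerful contrast, as the table in step 4 shows. Exact cancellation needs equal effects at both visits, the remark in 10.4 about cast removal does not name the PRWHE, and the shrinking gap in step 3 rests on an assumed third-week fall. All of this stands. It makes T2 a judgement rather than the only defensible primary test.

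**The interaction is not the main cause of low power.** A reader might blame it for the shortfall. At r = 0.5 it and the T2 contrast have the same 10%; the loss comes mostly from entering a standardized difference as f. Nor is 80% impossible for every contrast: the interaction gets there at r of about 0.97, which is implausible but not excluded by the text.

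**Error inflation is conditional.** It would be too strong to say that the plan has a false-positive rate of 9-12%. If the per-visit PRWHE results were read only after a significant 5% multivariate test, false positives under no effect at either visit could not exceed 5%. Section 9.3 states no such gate, so neither reading is fixed by the plan.

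**Conclusion.** The point holds and should be corrected before the results are analysed. It has three parts:

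- **Sized test.** It ignores any part of the PRWHE benefit that is already present at T1 and persists to T2. This follows from the design and needs no assumption about SD or r.
- **No primary contrast.** The contrasts that retain such a benefit are planned but unranked and unsized. If T1 and T2 are each tested at 5% without a gate, the false-positive rate is about 7-9%, or 11-12% with the interaction added, for r between 0.5 and 0.9.
- **Stated power.** The 80% applies to a difference in change of about 21 points at the default r = 0.5, not to 5. This is the larger numerical error. For 5 points at T2 the power is about 10% at SD 26.13, rising to 22% if the T2 SD were as low as 15.

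The first two parts concern what is tested and the third what was promised. Correcting f alone would leave the interaction blind to a lasting early benefit; changing the contrast alone would leave the power overstated.

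**What to change.** 1. **In 9.3, name one primary test:** the between-group difference in PRWHE at T2, two-sided 5%, from a pre-specified linear model that neither subtracts nor adjusts for T1. T2 is where 4.4 places its 5-point target, and this contrast keeps both a lasting early benefit and a later one. Adjust only for age and fracture type, which are fixed before allocation. Leave out involvement of the casted hand, which arises during training. Use the VMIQ score (completed after allocation and after the arm-specific letters, 7.2 and 10.2), occupation and sport only in sensitivity analyses. State that the Mann-Whitney switch in 9.2 does not apply to the primary test, and keep Mann-Whitney as a sensitivity analysis.
2. **Make everything else secondary:** the T1 difference, the overall group effect, the interaction, the MANOVA and the other outcomes.
3. **In 4.4, keep N = 52** and replace the interaction setting and the 80% statement with the unadjusted power of the T2 contrast: about 10% for 5 points (11% for 5.3), and 80% only for about 20.7 points at SD 26.13. Add the SD 20 and SD 15 results from step 5, with the reason for the range. State that 0.20 was a standardized difference and not f, and that the trial is not powered for the one-week lead.

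**Cost.** An amendment to 4.4 and 9.3, with one sentence in 9.2; no change to visits or N. The stated power becomes much less favourable. If the benefit in truth arises only after T1 and r exceeds 0.5, the T2 contrast gives up power relative to the interaction, for example 10% against 19% at r = 0.8.
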